# STATISTICAL ANALYSIS PLAN

[REDACTED]

[REDACTED]

[REDACTED]

- [REDACTED]
- [REDACTED]
- [REDACTED]
- [REDACTED]
- [REDACTED]
- [REDACTED]
- [REDACTED]
- [REDACTED]

[REDACTED]

[REDACTED]

[REDACTED]

[REDACTED]

- [REDACTED]
- [REDACTED]
- [REDACTED]
- [REDACTED]
- [REDACTED]
- [REDACTED]
- [REDACTED]
- [REDACTED]

[REDACTED]

[REDACTED]

[REDACTED]

### 3. STATISTICAL SOFTWARE

All statistical outputs (summary tables and data listings) will be generated using SAS® version 9.4 or later.

[REDACTED]

# STATISTICAL ANALYSIS PLAN

## 4. LAYOUT OF THE STATISTICAL TABLES

### 4.1. Quantitative variables

#### 4.1.1. Without group (Type 1)

	N	Missing	Mean	S.D.	Median	Min,Max	Q1-Q3
Variable	XX	XX	XX,X	XX,X	XX,X	XX,X , XX,X	XX,X - XX,X

#### 4.1.2. By group (Type 2)

	Group	N	Missing	Mean	S.D.	Median	Min,Max	Q1-Q3
Variable	Group 1	XX	XX	XX,Z	XX,Z	XX,Z	XX,Z , XX,Z	XX,Z - XX,Z
	Group 2	XX	XX	XX,Z	XX,Z	XX,Z	XX,Z , XX,Z	XX,Z - XX,Z
	...	...	...	...	...	...	...	...
	Total*	XX	XX	XX,Z	XX,Z	XX,Z	XX,Z , XX,Z	XX,Z - XX,Z

### 4.2. Qualitative variables

#### 4.2.1. Without group (Type 3)

		POP (N=XX)
Variable	N	XX
	Mod 1	XX (XX.X%)
	IC 95% (Mod 1)*	[XX.X ; XX.X]
	...	...
	Mod n	XX (XX.X%)
	IC 95% (Mod n)*	[XX.X ; XX.X]
	Missing	XX

\* if needed

# STATISTICAL ANALYSIS PLAN

FPR AAA 12-02

Page 13/17

## 4.2.1. By group (Type 4)

		Group			
		Group 1 (N=XX)	Group 2 (N=XX)	...	Total* (N=XX)
Variable	N	XX	XX	...	XX
	Mod 1	XX (XX.X %)	XX (XX.X %)	...	XX (XX.X %)
	IC 95% (Mod 1)*	[XX.X ; XX.X]	[XX.X ; XX.X]	...	[XX.X ; XX.X]
	...	...	...	...	...
	Mod n	XX (XX.X %)	XX (XX.X %)	...	XX (XX.X %)
	IC 95% (Mod n)*	[XX.X ; XX.X]	[XX.X ; XX.X]	...	[XX.X ; XX.X]
	Missing*	XX	XX	...	XX

\* if needed

## 4.2.2. Conditional variables (Type 5)

Variable / Conditional variable	Population* (N=XX)	Group 1* (N=XX)	...	Group n* (N=XX)
Mod 1	XX (XX.X %)	XX (XX.X %)	...	XX (XX.X %)
Conditional Mod 1	XX (XX.X %)	XX (XX.X %)	...	XX (XX.X %)
...	...	...	...	...
Conditional Mod n	XX (XX.X %)	XX (XX.X %)	...	XX (XX.X %)
...	...	...	...	...
Mod n	XX (XX.X %)	XX (XX.X %)	...	XX (XX.X %)
Conditional Mod 1	XX (XX.X %)	XX (XX.X %)	...	XX (XX.X %)
...	...	...	...	...
Conditional Mod n	XX (XX.X %)	XX (XX.X %)	...	XX (XX.X %)

\* if needed

## 4.3. Other type of tables

### 4.3.1. Flowchart (Type 6)

Populations / Reasons	SAF population	ITT Population
Baseline	XX (XX.X %)	XX (XX.X %)
Study exit reason 1*	XX (XX.X %)	XX (XX.X %)
Study exit reason 2*	XX (XX.X %)	XX (XX.X %)
...	...	...
5 Year FUP*	XX (XX.X %)	XX (XX.X %)

\* if any

# STATISTICAL ANALYSIS PLAN

FPR AAA 12-02

Page 14/17

## 4.3.2. Adverse Events (Type 9)

[figure not shown]
Adverse events	POP (N=XX)		
	NAE (1)	n (2)	% (3)
AE type 1	XX	XX	XX.X
AE type 2	XX	XX	XX.X
...	XX	XX	XX.X
AE type n	XX	XX	XX.X

(1) : Number of adverse events

(2) : Number of patients

(3) :  $(n / N) * 100$  (N : number of patients)

## 4.3.3. Survival curve (Type 10)

STRATA: ——— Mod 1  
 ○ ○ ○ Censored Mod 1  
 - - - ...  
 ○ ○ ○ ...  
 - - - Mod n  
 ○ ○ ○ Censored Mod n

### Summary table

	Mod 1 (n=X)	...	Mod n* (n=X)
Nb of patients	X	...	X
Nb of patients with an event	X (XX.XX%)	...	X (XX.XX%)
Nb of patients without an event	X (XX.XX%)	...	X (XX.XX%)
Survival rate	XX %	...	XX %
Progression-Free survival (days)		...	
Median	XX	...	XX
(95% CI)	(XX, XX)	...	(XX, XX)
25th-75th percentile	XX.X – XX.x	...	XX.X – XX.x
Range	X - X	...	X - X

\* If any

## **5. TABLE OF CONTENTS**

### **5.1. Tables**

#### **5.1.1. Patient Disposition**

Table 1 : Patients status by sites (Type 4)

Table 2 : Study flowchart (Type 6)

Table 3 : Withdrawals and study exit reasons (Type 3)

Table 4 : Study durations (days) (Type 1)

#### **5.1.1. Patient Characteristics**

##### *5.1.1.1. Baseline*

Table 5 : Age at surgery (years) (Type 1)

Table 6 : Age classes at surgery (Type 3)

Table 7 : Gender (Type 3)

Table 8 : Weight (kg) (Type 1)

Table 9 : Height (cm) (Type 1)

Table 10 : BMI (Type 1)

Table 11 : Medical history (Type 3)

Table 12 : ASA classification (Type 3)

Table 13 : Surgical risk (Type 3)

Table 14 : Maximal aneurysm diameter (mm) (Type 1)

Table 15 : Maximal aneurysm diameter classes (Type 3)

Table 16 : Angle between proximal aortic neck and main axis of the AAA (degrees) (Type 1)

Table 17 : Proximal neck length (mm) (Type 1)

Table 18 : Proximal neck diameter (mm) (Type 1)

Table 19 : Proximal aortic neck characteristics (Type 3)

##### *5.1.1.2. Procedure*

Table 20 : Implantation main indication (Type 3)

Table 21 : Duration of procedure (minutes) (Type 1)

Table 22 : GORE® EXCLUDER® AAA Endoprosthesis bifurcated (Type 3)

Table 23 : Access type (Type 3)

Table 24 : Type of anesthesia used (Type 3)

Table 25 : Volume of contrast medium (ml) (Type 1)

Table 26 : Time under fluoroscopy (minutes) (Type 1)

Table 27 : Procedure outcome and failure details (Type 3)

Table 28 : Related surgical/endovascular procedures (Type 3)

Table 29 : Surgical complications (Type 3)

Table 30 : Abnormalities observed (Type 5)

Table 31 : Endoleak (Type 5)

Table 32 : Stay in Intensive Care Unit (hours) (Type 1)

# STATISTICAL ANALYSIS PLAN

## 5.1.2. Endpoint analysis

### 5.1.2.1. Primary Analysis

Table 33 : Mortality survival analysis (Type 10)

### 5.1.2.2. Secondary Analysis

Table 34 : Surgical conversion rate (Type 3)

Table 35 : Mortality related to aneurysm survival analysis (Type 10)

Table 36 : Diameter increase survival analysis (Type 10)

Table 37 : Endoleak survival analysis – overall (Type 10)

Table 38 : Endoleak survival analysis – type I (Type 10)

Table 39 : Endoleak survival analysis – type II (Type 10)

Table 40 : Endoleak survival analysis - type III (Type 10)

Table 41 : Migration survival analysis – overall (Type 10)

Table 42 : Migration survival analysis – distal (Type 10)

Table 43 : Migration survival analysis - proximal (Type 10)

Table 44 : Re-intervention survival analysis (Type 10)

[REDACTED]

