3.3 Evaluation Criteria

These criteria are measured postoperatively or within one month after surgery, at 6 months, 12 months and then annually for 5 years, with an annual report issued to be submitted to the French National Authority for Health:

- Overall mortality rate,
- Mortality rate related to the aneurysm,
- Evolution of the diameter of the aneurysm
- Rate of Endoleaks for Type I, II and III
- Migration rate,
- Rate of surgical conversion,
- Rate of endovascular or surgical re-intervention.

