3.4 Evaluation Parameters

General Data

- Age
- Gender
- Diameter of Abdominal Aortic Aneurysm
- Patient status (normal or high surgical risk according to the Afssaps criteria, Appendices 3 and 4)
- All references and evolution of the range of the GORE® EXCLUDER Endoprosthesis®

Data related to the procedure (at all control times):

- Death from all causes
- Aneurysm-related death
- Evolution of the diameter of the aneurysm
- Types I, II and III endoleak
- Migration
- Surgical conversion
- Re-intervention related to the initial procedure

Definitions :

Death related to the aneurysm shall be defined as any death occurring as a result of a ruptured Abdominal Aortic Aneurysm or following any procedure intended to treat Abdominal Aortic Aneurysm.

If the death occurred within 30 days of any procedure intended to treat Abdominal Aortic Aneurysm, then it will be considered as related to the aneurysm unless proven otherwise. Deaths occurring beyond 30 days of any procedure intended to treat Abdominal Aortic Aneurysm and that are related to the procedure should be considered as related to the aneurysm.

Distal migration is defined by a distal displacement strictly greater than 10 mm. Proximal migration is defined either by proximal displacement strictly greater than 10 mm, or by proximal displacement which covers one of the renal arteries; the reference examination being the first postoperative CT performed.

An increased aneurysm diameter is defined as an increase strictly greater than 5 mm of the largest measurable diameter of the aneurysm; the reference diameter being the diameter of the first post-operative check-up.

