6.2.2 Criteria Studied

Main analyses:

The criteria studied are as follows:

- Death from all causes
- Aneurysm-related death
- Evolution of the diameter of the aneurysm.
- Types I, II and III endoleaks
- Migration
- Surgical conversion
- Re-intervention related to the initial procedure

Definitions :

- Death related to the aneurysm shall be defined as any death occurring as a result of a ruptured Abdominal Aortic Aneurysm or following any procedure intended to treat Abdominal Aortic Aneurysm.
If the death occurred within 30 days of any procedure intended to treat Abdominal Aortic Aneurysm, then it will be considered as related to the aneurysm unless proven otherwise. Deaths occurring beyond 30 days of any procedure intended to treat Abdominal Aortic Aneurysm and that are related to the procedure should be considered as related to the aneurysm.
- Distal migration is defined by a distal displacement strictly greater than 10mm. Proximal migration is defined either by proximal displacement strictly greater than 10mm, or by proximal displacement which covers one of the renal arteries; the reference examination being the first postoperative CT performed.

- An increase in the diameter of the aneurysm is defined by an increase strictly greater than 5 mm of maximum diameter of the highest measurable diameter of the aneurysm; the reference diameter being the diameter of the first post-operative check-up.

Each of the rates that match the Study criteria will be analyzed by calculating frequency distributions and bilateral confidence intervals of 95% (IC95) associated.

Event rates over time are described by survival curve according to the Kaplan-Meier method and the related Kaplan-Meier estimators will be calculated.

Additional Analyses:

All the analyzes may be stratified by center if recruitment in each center participating in the study is sufficient for such analyzes to be of interest. However, it must be emphasized that this Protocol in no way aims to compare the centers.

For exploratory purposes, the study criteria will also be analyzed depending on patient baseline characteristics:

- Age (in categories)
- Gender
- Diameter of Abdominal Aortic Aneurysm
- Patient status (normal or high surgical risk according to the Afssaps criteria, Appendices 3 and 4)

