### 2.4.3.2. Secondary Analyses

The surgical conversion rate during procedure and the corresponding 95% confidence interval will be provided.

The following parameters will be presented using the Kaplan-Meier survival curves:

- Mortality related to the aneurysm
- Aneurysm diameter evolution
- Endoleak complication, for each type (I, II and III)
- Device migration overall and by type (distal, proximal)
- Re-intervention

For the parameters “Aneurysm diameter evolution”, “Endoleak complication” and “Device migration”, the date to be used for the survival analysis is the date of the first visit where the parameter is reported. Only events occurring up to 5 years (1826 days) of follow-up will be analyzed for these survival curves.

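### In the readable SAP, evolution of the aneurysm diameter is analysed as time to first increase, and no visible table shows change in millimetres or shrinkage by visit

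*SAP*

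**What the plan says.** Protocol 3.3 lists "Evolution of the diameter of the aneurysm" among the criteria, with no direction attached, and sets the timing: "These criteria are measured postoperatively or within one month after surgery, at 6 months, 12 months and then annually for 5 years".

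The protocol defines one diameter event. Section 3.4 has "An increased aneurysm diameter is defined as an increase strictly greater than 5 mm of the largest measurable diameter of the aneurysm", with "the reference diameter being the diameter of the first post-operative check-up". Section 6.2.2 repeats it: "An increase in the diameter of the aneurysm is defined by an increase strictly greater than 5 mm". Neither section defines a decrease or a stable diameter.

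On analysis, Protocol 6.2.2 asks for frequencies with 95% confidence intervals as well as Kaplan-Meier estimates. Protocol 6.2.1 adds a general rule for patient data and descriptive follow-up data: quantitative items are summarised by mean, SD, median, quartiles, range and number missing. It does not name the diameter.

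SAP 2.4.3.2 places diameter evolution in the list introduced by "The following parameters will be presented using the Kaplan-Meier survival curves". The event is dated at the first visit that reports it, and events count up to 1826 days. The matching output is "Table 36 : Diameter increase survival analysis (Type 10". As a measurement, the diameter appears in the visible shells only at baseline: "Table 14 : Maximal aneurysm diameter (mm) (Type 1", and Table 15, which gives classes.

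**The concern.** The criterion is called evolution in the protocol and in SAP 2.4.3.2, but the visible output reports increase. A time-to-first-increase curve shows one adverse tail of the distribution of change. A sac that has shrunk, a sac that has not changed and a sac that has grown by exactly 5 mm are all recorded as having no event. A sac that grows past the threshold and later regresses remains an event.

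The study exists to document, among other things, how the aneurysm evolves over 5 years, in results that go to the regulator each year. If the curve is all that is reported for this criterion, the regulator learns how often sacs grew, but not how often they shrank or by how much. The repeated measurements that would show this are already scheduled.

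**Working it through.** The plan states no figure for this criterion, so there is none to reproduce. The check compares the criterion with the visible outputs, then illustrates how much the curve leaves open.

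**Step 1: criterion against output.**

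| Element | Protocol | Readable SAP |
|---|---|---|
| Quantity | Evolution of diameter, no direction (3.3) | Time to first increase (2.4.3.2, Table 36) |
| Time points | Each scheduled follow-up (3.3) | One event date per patient |
| Threshold | Increase strictly above 5 mm (3.4, 6.2.2) | Not stated |
| Reference | First post-operative check-up | Not stated; Tables 14 and 15 are pre-implant |
| Decrease, stability | Not defined | Not tabulated |

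Tables 14 and 15 cannot stand in for the reference value, because SAP 2.1.1 takes baseline as the last observation before the device is used.

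**Step 2: what the Type 10 layout can hold.** The SAP 4.3.3 shell has numbers with and without an event, a survival rate, and time percentiles. It has no millimetre values, no visits and no category for a decrease. Two cohorts with the same increases at the same times, 10% of patients in each, would give the same Table 36 even if 60% of one and 10% of the other shrank by more than 5 mm.

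**Step 3: how much shrinkage one rate of increase allows.** Assume that change at a given visit is normal with standard deviation SD, and fix the share p above +5 mm.

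- Mean change = 5 − z(1−p) × SD
- Share shrinking by more than 5 mm = Φ((−5 − mean)/SD)

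For p = 10%, z = 1.2816:

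| SD (assumed) | Mean change | Share shrinking > 5 mm |
|---|---|---|
| 4 mm | 5 − 5.13 = −0.13 mm | Φ(−1.22) = 11% |
| 8 mm | 5 − 10.25 = −5.25 mm | Φ(0.03) = 51% |
| 12 mm | 5 − 15.38 = −10.38 mm | Φ(0.45) = 67% |

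Over the same SDs, p = 5% gives 20% to 79% and p = 20% gives 5% to 50%. This is a single-visit illustration, whereas Table 36 accumulates first events over visits. The SDs and the normal shape are not in the documents.

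**Step 4: precision of a descriptive table.** The 95% half-width for the mean change is 1.96 × SD/√n. With n = 110 assumed measured at 5 years, √110 = 10.49:

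- SD 6: 11.76/10.49 = 1.1 mm
- SD 8: 15.68/10.49 = 1.5 mm
- SD 10: 19.60/10.49 = 1.9 mm

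For a share of 30% to 50%, 1.96 × √(p(1−p)/n) gives about 7 percentage points if all 180 patients are measured and 9 to 10 points at n = 100.

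**The case against.** The strongest objection is that part of the SAP cannot be read. The text after 2.4.3.2, the tables after Table 44 and several listings are blacked out, and sections 2.1.3 to 2.3.1 appear in the contents list but not in the readable text. A reader might infer that shrinkage and size of change will never be reported, pointing out that the contents list puts the safety analysis straight after the endpoint tables. The documents do not support that inference:

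- The contents list stops at three-level headings. It omits 2.4.3.1, 2.4.3.2, 5.1.2.1 and 5.1.2.2, which exist, so it cannot exclude a redacted 2.4.3.3 or 5.1.2.3.
- SAP 2.4.3 describes the secondary endpoints as safety parameters, so a redacted safety section could also cover diameter.
- The Type 2 layout (quantitative, by group) is used by none of Tables 1 to 44, and SAP 2.1.1 defines visit-level data that a survival curve does not need. Both would suit a by-visit summary, though either could be left over from a template.

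This stands, and it limits the point to what can be read. It does not remove it: the readable text that names this parameter gives it a survival curve and nothing else.

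Two further objections hold in part. Protocol 6.2.1 and 6.2.2 already promise descriptive statistics and frequencies, and the SAP says that it adds detail to the protocol. However, no visible SAP table carries this through for diameter after baseline. Also, the 5 mm event is the protocol's own definition, so Table 36 follows the protocol and is not a mistake. Yet the protocol defines an increase; it does not say that evolution means increase alone.

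**Conclusion.** The point holds for the readable plan. Diameter evolution is analysed as time to first increase, strictly above 5 mm by the protocol's definition, and no visible table reports post-baseline diameter, change in millimetres, or shrinkage by visit. Table 36 alone cannot separate shrinking sacs from unchanged ones. Whether the full plan lacks such a table is not established.

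No planned result is biased: Table 36, the primary mortality analysis and the sample size are unaffected. What is at stake is whether the study describes the criterion it was asked to document. That a one-sided event cannot show shrinkage needs no assumption. The percentages in the working, the 110 patients and the SDs are illustrative assumptions and say nothing about this cohort's actual results.

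**What to change.** First check the redacted sections. If they hold no by-visit diameter table, keep Table 36 and add one descriptive endpoint table giving, at each scheduled visit:

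- maximal diameter, and change from the first post-operative check-up: n, missing, mean, SD, median and quartiles, with a 95% CI for the mean change;
- the shares with an increase above 5 mm, a change within 5 mm and a decrease above 5 mm, each with a 95% CI, among patients measured.

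The stable and decrease categories are not in the protocol. They should be stated in advance as reporting categories that mirror its 5 mm threshold.

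Label the table as describing only patients alive and imaged at that visit, and note the imaging modality, since Protocol 3.2 allows MRI or Doppler where contrast CT cannot be done. Use values measured at the visit: the SAP 2.1.1 rule, which takes the last observation on or before the time point, could otherwise fill a missed visit with an older measurement.

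The cost is one table in the existing Type 1 and Type 3 layouts, with the confidence interval for the mean change added. It needs no new data, no change to the sample size and no change to patient care.

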## 5.2. Listings

### 5.2.1. Patient Disposition

Listing 1: Withdrawals

Listing 2: Deviations as reported by investigators

[REDACTED]

# STATISTICAL ANALYSIS PLAN

## 5.2.2. Patient Characteristics

### 5.2.2.1. Procedure

Listing 3: Implantation main indication

Listing 4: Patient not implanted with GORE® EXCLUDER® AAA Endoprosthesis bifurcated

Listing 5: Associated surgical/endovascular procedures

Listing 6: GORE® EXCLUDER® AAA Endoprosthesis details

[REDACTED]

[REDACTED]

[REDACTED]

[REDACTED]
